## 11 Technical Details

All analyses are performed using IBM SPSS Statistics, version 24 or newer (IBM Corp., N.Y., USA) and R Statistics, version 3.6 or newer.

## 12 Sample Tables for Data Reporting

### 12.1 Demographic data PAD all stages in study groups 1 and 2

Baseline characteristics-patients with PAD	
Age	Mean $\pm$ SD
Sex	n (% of total n)
Risk factors Smoking, arterial hypertension, lipid abnormalities, diabetes mellitus, obesity, positive familiar history	n (% of total n)
Relevant underlying diseases CHD, CHF, atrial fibrillation, CKD, carotid artery stenosis, previous cerebrovascular event	n (% of total n)
Previous vascular surgery/intervention	n (% of total n)
Current Medication	n (% of total n)
Clinical scoring ABI Pulse status lower extremity Fontaine stage, Rutherford stage	Mean $\pm$ SD n (% of total n) n (% of total n)
CCDS Morphological flow profile, Presence of relevant stenosis PSV	n (% of total n) Mean $\pm$ SD
Angiography TASC score	n (% of total n)
MSOT Lipid content, collagen content	Mean $\pm$ SD

### 12.2 Demographic data healthy control collective in study groups 1 and 2

Baseline characteristics-healthy collective	
Age	Mean $\pm$ SD
Sex	n (% of total n)
Risk factors Smoking, arterial hypertension, lipid abnormalities, diabetes mellitus, obesity, positive familiar history	n (% of total n)
Relevant underlying diseases CHD, CHF, atrial fibrillation, CKD, carotid artery stenosis, previous cerebrovascular event	n (% of total n)
Previous vascular surgery/intervention	n (% of total n)
Current Medication	n (% of total n)

Clinical scoring		
ABI	Mean $\pm$ SD	
Pulse status lower extremity	n (% of total n)	
Fontaine stage, Rutherford stage	n (% of total n)	
CCDS		
Morphological flow profile, Presence of relevant stenosis	n (% of total n)	
PSV	Mean $\pm$ SD	
MSOT		
Lipid content, collagen content	Mean $\pm$ SD	

### 12.3 Data correlation PAD all stages in study group 1 and 2

All MSOT parameters have two values: “*Pre*” means before gait exposure and “*Post*” means after gait exposure.

Parameters	Hbtot	HbO 2	Hb	Difference HbO 2 /Hb	Values at 800 nm
Angiography TASC score	Correlation	Correlation	Correlation	Correlation	Correlation
Clinical scoring ABI Walking distance Fontaine stage, Rutherford stage	Correlation	Correlation	Correlation	Correlation	Correlation
CCDS Morphological flow profile, relevant stenosis PSV	Correlation	Correlation	Correlation	Correlation	Correlation

### 12.4 Data correlation healthy control collective in study groups 1 and 2

All MSOT parameters have two values: “*Pre*” means before gait exposure and “*Post*” means after gait exposure. If not explicitly mentioned, the following assumes the analysis of both values.

Parameters	Hbtot	HbO 2	Hb	Difference HbO 2 /Hb	Values at 800 nm

Clinical scoring ABI Walking distance Fontaine stage, Rutherford stage	Correlation	Correlation	Correlation	Correlation	Correlation
CCDS Morphological flow profile, relevant stenosis PSV	Correlation	Correlation	Correlation	Correlation	Correlation

## 12.5 Samples for PAD clinical scoring

Disease Severity – grouping according to Fontaine classification

Parameters	Healthy	PAD IIa	PAD IIb	PAD III	PAD IV	pvalue	ANOVA
Angiography TASC score	Value not collected	n (% of total n)					
CCDS Morphological flow profile, relevant stenosis PSV	n (% of total n) Mean ±SD						
Clinical scoring ABI Walking distance	Mean ±SD						
Hbtot_Pre HbO2_Pre Hb_Pre Difference HbO2_Pre/Hb_Pre Values at 800 nm Pre	Mean ±SD						
Hbtot_Post HbO2_Post Hb_Post Difference HbO2_Post/Hb_Post Values at 800 nm Post							

Disease severity – grouping according to Fontaine classification

Parameters	Sensitivity	Specificity
Angiography TASC score	%	%
Clinical scoring ABI Walking distance	%	%
CCDS Morphological flow profile, relevant stenosis PSV	%	%
Hbtot_Pre HbO2_Pre Hb_Pre Difference HbO2_Pre/Hb_Pre Values at 800 nm Pre	%	%
Hbtot_Post HbO2_Post Hb_Post Difference HbO2_Post/Hb_Post Values at 800 nm Post		

Disease severity – grouping according to Rutherford classification

Parameters	Healthy	Categor y 1	Categor y 2	Categor y 3	Categor y 4	Categor y 5	Categor y 6	pvalue	ANOV A
------------	---------	----------------	----------------	----------------	----------------	----------------	----------------	--------	-----------

| Angiography
TASC score  | Value not
collected             | n (% of
total n)                |  |  |
|--|------------------------------------|------------------------------------|------------------------------------|------------------------------------|------------------------------------|------------------------------------|------------------------------------|------------------------------------|--|--|
| CCDS
Morphological flow
profile,
relevant stenosis
PSV   | n (% of
total n)
Mean
±SD |  |  |
| Clinical scoring
ABI
Walking distance  | Mean
±SD                        |  |  |
| Hbtot_Pre
HbO2_Pre
Hb_Pre
Difference
HbO2_Pre/Hb_Pre
Values at 800 nm
Pre

Hbtot_Post
HbO2_Post
Hb_Post
Difference
HbO2_Post/Hb_Post
Values at 800 nm
Post | Mean
±SD                        |  |  |

## Disease severity – grouping according to Rutherford classification

Parameters	Sensitivity	Specificity
Angiography TASC score	%	%
Clinical scoring ABI Walking distance	%	%
CCDS Morphological flow profile, relevant stenosis PSV	%	%
Hbtot_Pre HbO2_Pre Hb_Pre Difference HbO2_Pre/Hb_Pre Values at 800 nm Pre  Hbtot_Post HbO2_Post Hb_Post Difference HbO2_Post/Hb_Post Values at 800 nm Post	%	%

## 12.6 Samples for PAD angiographic scoring

Severity of stenosis – grouping according to combined TASC subgroups

Parameters	I	II	III	IV	p-value	ANOVA
CCDS Morphological flow profile, relevant stenosis PSV	Mean ±SD	Mean ±SD	Mean ±SD	Mean ±SD		
Clinical scoring ABI Walking distance Fontaine stage, Rutherford stage	Mean ±SD	Mean ±SD	Mean ±SD	Mean ±SD		
Hbtot_Pre HbO2_Pre Hb_Pre Difference HbO2_Pre/Hb_Pre Values at 800 nm Pre  Hbtot_Post HbO2_Post Hb_Post Difference HbO2_Post/Hb_Post Values at 800 nm Post	Mean ±SD	Mean ±SD	Mean ±SD	Mean ±SD		

Severity of stenosis – grouping according to combined TASC subgroups

Parameters	Sensitivity	Specificity
Clinical scoring ABI Walking distance Fontaine stage, Rutherford stage	%	%
CCDS Morphological flow profile, relevant stenosis PSV	%	%
Hbtot_Pre HbO2_Pre Hb_Pre Difference HbO2_Pre/Hb_Pre Values at 800 nm Pre  Hbtot_Post HbO2_Post Hb_Post Difference HbO2_Post/Hb_Post Values at 800 nm Post	%	%

## 12.7 Samples for PAD CCDS scoring

Stenosis severity – grouping according to CCDS scoring

Parameters	CCDS relevant stenosis	CCDS no relevant stenosis	p-value	ANOVA
Angiography TASC score	Mean ±SD	Mean ±SD		

Clinical scoring ABI Walking distance Fontaine stage, Rutherford stage	Mean ±SD	Mean ±SD		
Hbtot_Pre HbO2_Pre Hb_Pre Difference HbO2_Pre/Hb_Pre Values at 800 nm Pre  Hbtot_Post HbO2_Post Hb_Post Difference HbO2_Post/Hb_Post Values at 800 nm Post	Mean ±SD	Mean ±SD		

## Stenosis severity – grouping according to CCDS scoring

Parameters	Sensitivity	Specificity
Clinical scoring ABI Walking distance Fontaine stage, Rutherford stage	%	%
Angiography TASC score	%	%
Hbtot_Pre HbO2_Pre Hb_Pre Difference HbO2_Pre/Hb_Pre Values at 800 nm Pre  Hbtot_Post HbO2_Post Hb_Post Difference HbO2_Post/Hb_Post Values at 800 nm Post	%	%

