## 6.2 Secondary targets:

- Oxygenation of the muscle, determination of oxygenated, deoxygenated hemoglobin, determination of lipid signal, determination of collagen signal
  - *These targets are measured non-invasively by MSOT*
- Flow profile of the A. femoralis communis and A. poplitea determined by CCDS
- ABI
- Actual walking distance standardized by treadmill examination
- Stage of PAD according to Fontaine and Rutherford
- Age, sex, risk factors for PAD
  - *These target values are either available in the electronic patient file or they are collected at presentation for the study.*
- Relevant underlying diseases
  - *This target values are either available in the electronic patient file or they are collected at presentation for the study.*
- Relevant previous operations
  - *This target values are either available in the electronic patient file or they are collected at presentation for the study.*
- Current medication
  - *This target value is either available in the electronic patient file or is collected at presentation for the study.*

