### **3.2 Purpose of the Analysis**

This analysis will assess capability of MSOT in comparison to the gold standard (angiography) and the clinical PAD stage as a reference standard to predict the severity of PAD. If necessary, the angiographic findings will be combined with the CCDS measures in order to define a flow relevant stenosis.

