- *individuals with unremarkable radiological findings according to TASC in each of the aortoiliacal (AI), femoropopliteal (FP) and infrapopliteal (IP) levels*

aTASC 2: aTASC type with good chances for collateralization:

- *due to mild findings in AI levels and any findings in FP levels which is considered a potential for collaterals through A. profunda branches.*

aTASC 3: aTASC type with poor chances for collateralization:

- *all combination of AI and FP TASC patterns with theoretically poor chances for collateralization. Here severe findings at AI level are summarized because of poor collateralization capability via A. profunda branches.*

aTASC 1	aTASC 2	aTASC 3
combination of 1. no AI TASC findings 2. no FP TASC findings 3. no IP TASC findings	combination of 1. AI no TASC or TASC A/B 2. FP no TASC or TASC A/B/C/D 3. any IP TASC findings 4. at least TASC A/B in 1. or 2.	combination of 1. AI TASC C/D 2. FP no TASC or TASC A/B/C/D 3. any IP TASC findings

CCDS 	X	Whether a flow-relevant stenosis is present in the examined vessels is decided by an independent reader
ABI 	X	
Clinical scores 	X	

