**CCDS:**

Morphological flow profile and PSV of CFA and A. poplitea

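### SAP Table 12.7 scores angiography and MSOT against duplex of a few arterial sites, so correct positives can be counted as false positives in that table

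*SAP*

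**What the plan says.** SAP 12.7 has two shells. The first splits subjects by the duplex verdict; its second column is "CCDS no relevant stenosis". The second, "Stenosis severity – grouping according to CCDS scoring", asks for sensitivity and specificity of the clinical measures, of "Angiography TASC score", and of ten MSOT readouts (five before and five after exercise).

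The duplex verdict is defined in SAP 5.4: "Whether a flow-relevant stenosis is present in the examined vessels is decided by an independent reader". The recorded measurements are "Morphological flow profile and PSV of CFA and A. poplitea". Protocol 6.2 names the same two sites: "Flow profile of the A. femoralis communis and A. poplitea determined by CCDS". Protocol 9.2 is wider, describing a scan of the femoral as well as the popliteal arteries. Neither document gives a PSV limit or waveform rule for a relevant stenosis.

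On the reference standard, SAP 3.2 states: "This analysis will assess capability of MSOT in comparison to the gold standard (angiography) and the clinical PAD stage as a reference standard". The sentence after it, like SAP 4.2 and 7.3, brings CCDS in only as a supplement to angiography where needed. The TASC and aTASC definitions in SAP 5.4 cover the aorta, the common and external iliac arteries, the superficial femoral artery and the infrapopliteal level, besides the two duplex sites.

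In SAP 12.5 the angiography entry for healthy subjects reads "Value not collected", yet the accuracy shells of 12.5 request a specificity for TASC.

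**The concern.** Column headings of sensitivity and specificity make the grouping variable the truth. In 12.7 that variable is a test which the plan elsewhere treats as a supplement, while the declared gold standard appears as one of the tests being graded.

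The duplex verdict also covers less of the arterial tree than angiography does. The most severe class, aTASC 3, is defined by aorto-iliac TASC C or D findings, a level that neither document lists among the duplex sites. If such a leg is read as having no relevant stenosis in the examined vessels, an MSOT or angiographic positive is entered as an error.

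The same happens where duplex is unreliable. Protocol sections 2 and 4 and SAP 3.1 say that CCDS can give inadequate results in diabetes or renal failure, and that MSOT is meant to fill this gap. Where MSOT is right and duplex fails, 12.7 charges the error to MSOT.

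At stake are a reported accuracy for the gold standard, and a reported specificity for MSOT, that partly reflect which arteries duplex covered.

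**Working it through.** The plan states no sensitivity, specificity or duplex miss rate, so there is no figure of its own to reproduce. The calculation below is an illustration.

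**Inputs**
- H = 33 controls and D = 66 diseased legs. SAP 6 arrives at about 33 for each of three groups (controls, stage II, stages III-IV), and 2 × 33 = 66.
- Se = Sp = 80% for MSOT against true disease (assumed).
- q = share of diseased legs that CCDS calls negative: 0%, 10%, 20%, 40% (assumed).
- CCDS calls every control negative, and MSOT is as sensitive in CCDS-negative diseased legs as in the others (both assumed).

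**MSOT specificity as 12.7 would report it**

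Apparent specificity = (H·Sp + D·q·(1 − Se)) / (H + D·q)

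| q | Reference negatives, 33 + 66q | MSOT negatives among them | Apparent specificity |
|---|---|---|---|
| 0% | 33.0 | 26.4 | 80% |
| 10% | 39.6 | 26.4 + 1.32 = 27.72 | 70% |
| 20% | 46.2 | 26.4 + 2.64 = 29.04 | 63% |
| 40% | 59.4 | 26.4 + 5.28 = 31.68 | 53% |

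At q = 20%, the 66 × 0.2 × 0.8 = 10.56 correct MSOT positives are booked as false positives.

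**Variations**
- MSOT at 90%/90%: 30.36/39.6 = 77%, 31.02/46.2 = 67%, 32.34/59.4 = 54% for q = 10%, 20%, 40%.
- An angiogram that is always right (Se = Sp = 100%): 33/39.6 = 83%, 33/46.2 = 71%, 33/59.4 = 56%.
- SAP 5.2 instead expects about 200 subjects in five similar groups, so roughly 40 controls and 160 patients. At 80%/80%: q = 10% gives (32 + 3.2)/56 = 63%, and q = 20% gives (32 + 6.4)/72 = 53%.
- The 12.7 shells have no healthy column. If the table holds only patients with lesions, H = 0 and apparent specificity is 1 − Se = 20% for any q above zero.
- If MSOT is less sensitive in CCDS-negative legs, the loss shrinks. It vanishes when that sensitivity falls to 1 − Sp = 20%: (26.4 + 13.2 × 0.8)/46.2 = 80% at q = 20%.

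**The TASC row in 12.5**

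The accuracy shells of 12.5 state no dichotomy. The only one the SAP gives is controls against stages III/IV, in 9.3, where the controls are the only negatives. Their TASC is either not collected, and specificity cannot be computed, or it is set by the SAP 5.4 rule that places volunteers without angiography in aTASC 1, and specificity is 100% by rule. That rule uses a normal CCDS among its conditions, so scoring angiography against CCDS in 12.7 is also partly circular for these volunteers.

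**The case against.** The strongest defence is that Section 12 contains sample tables and that comparing MSOT with CCDS is a planned secondary objective. CCDS has a conditional role in the reference (SAP 3.2, 4.2, 7.3), and Table 12.6 already scores both CCDS and MSOT against the TASC subgroups. All of this stands. It justifies an MSOT-by-CCDS comparison, but not headings that make CCDS the truth, and it does not explain a row grading angiography against CCDS.

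A reader might infer that every lesion outside the common femoral and popliteal arteries is counted as no stenosis. The documents do not support that. The scan in Protocol 9.2 may include the superficial femoral artery. The flow profile is recorded too, and with no written criterion the reader may take an abnormal profile as a sign of a lesion upstream. The documents neither ensure nor exclude this.

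A reader might also infer that the validated accuracy of MSOT is compromised. It is not affected by this table: SAP 9.3 derives the cutpoint from controls against stages III/IV and carries it unchanged into study group 2.

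The size is hypothetical, as the miss rate and accuracies are assumed, and equal MSOT sensitivity in CCDS-negative legs may be generous if those legs have milder disease.

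**Conclusion.** The concern holds for this one table. As laid out, 12.7 reverses the declared order of the tests and can count correct positives as false positives, which biases specificity downward. Under the stated assumptions, an MSOT specificity of 80% would read 70%, 63% or 53% at miss rates of 10%, 20% or 40%. There is no distortion if CCDS misses nothing. The true miss rate cannot be obtained from the documents.

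The primary endpoint, the cutpoint and its validation, and Table 12.6 are unaffected. The change should be made before reporting, but the study does not depend on it. The TASC row in 12.5 is a smaller fault of the same kind: under the one contrast stated, its specificity is uncomputable or fixed in advance.

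**What to change.** - Drop the sensitivity and specificity shell of 12.7, since 12.6 already scores CCDS and MSOT against TASC. Alternatively, keep the MSOT-CCDS comparison and label it as agreement: a 2×2 table with positive and negative percent agreement, or kappa. It should not be restricted by lesion site, because MSOT measures calf muscle, whose perfusion reflects the combined aorto-iliac and femoro-popliteal findings (Protocol 5.1, footnote).
- Delete the TASC row from the sensitivity and specificity shells of 12.5 (Fontaine and Rutherford) and 12.7.
- Reconcile the vessels named in Protocol 9.2 with those in SAP 5.4, and write down the criterion by which the reader calls a stenosis relevant, including whether an abnormal flow profile alone counts.
- State whether healthy volunteers enter 12.7.

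The cost is an edit to table shells and a few sentences of definition. No new data or measurements are needed.
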